4.1 Inclusion Criteria

For inclusion in the study, all of the following inclusion criteria must be fulfilled:

1. Subjects who have consented to participate.
2. Subjects who have successfully completed the placebo-controlled 24-week study AV-101-002 without a treatment-limiting toxicity resulting in discontinuation of study drug.
3. Female subjects of childbearing potential who have agreed to continue to use a highly effective form of contraception during the LTE and for at least 30 days after completing or discontinuing study treatment (highly effective forms of contraception are described in [Section 7.8](#)).

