The Week 24 end of study visit of the parent study (AV-101-002) also represents the baseline visit for the LTE study (AV-101-003). The following assessments will be conducted/collected during the baseline visit of the LTE and at selected time points specified in the Schedule of Assessments (Table 1). Additional procedures deemed necessary as part of standard of care may be performed at the discretion of the Investigator. All missed visits and any performed procedures that are not protocol-specified activities must be documented in the subject's medical record and the appropriate eCRF. General considerations for study visits include, but are not limited to the following:

- No protocol waivers or exemptions are allowed.
- Immediate safety concerns should be discussed with the CRO Medical Monitor immediately upon occurrence or awareness to determine if the subject should continue or discontinue study drug.
- Adherence to the study design requirements, including those specified in the Schedule of Assessments, is essential and required for study conduct (see Section 6.7.1 for COVID-19 considerations).
- The Investigator will obtain written informed consent before the end of study visit for study AV-101-002 and as specified in Section 9.1.3 (Informed Consent Process). Upon the subject's agreement, their primary health care provider should be informed about the subject's enrollment in the study.
- Order of Procedures:
 - Health-related QoL assessments should be performed prior to all other study procedures.
 - Vital signs should be collected prior to blood draws. Blood samples for NT-proBNP levels should be collected prior to the 6MWT.
 - All other study assessments should also be performed, according to the Schedule of Assessments (Table 1).
- **Unscheduled visits:** may occur at any time during the study with the assessments to be performed according to the Investigator's judgment. Unscheduled visits may also be necessary for study drug dispensing following temporary withdrawal as described in Sections 6.7 and 7.7.

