6.8 Discontinuation of Study Drug and Subject Discontinuation/Withdrawal

6.8.1 Discontinuation of Study Drug

At the time of early study drug discontinuation subjects may elect to (1) discontinue from the study and agree to telephone contacts per the visit schedule, or (2) discontinue from the study, and withdraw consent to be contacted in the future for further collection of study-related data.

For subjects who withdraw from or are withdrawn from taking the study drug, every attempt should be made to follow the subject for long term outcomes. However, if a subject withdraws consent to be contacted, they must complete the Early Discontinuation (ED) Visit within 14 days of AV-101 discontinuation, and then the Safety Follow-Up visits as described in [Section 6.2.2](#) and [6.2.4](#).

For subjects who are lost to follow-up, or who died, Safety Follow-up Visits may not be possible. In any case, the appropriate eCRF section must be completed.

The subject must be discontinued from taking study drug in the event of any of the following:

Examples:

- Enrollment despite violation of an inclusion or exclusion criterion which, in the Investigator’s and/or Sponsor’s opinion, makes discontinuation of the subject necessary.
- Occurrence of an AE/SAE that makes discontinuation of study drug desired or considered necessary by the Investigator and/or the subject.
- Participation in any other interventional study during the duration of this study for which the Investigator considers discontinuation of the AV-101 necessary.
- Occurrence of pregnancy (for further details in case of pregnancy, refer to [Section 7.8](#)).
- If disease activity is considered unacceptably high and treatment escalation beyond permitted medication changes ([Section 5.9.1](#)) is warranted in the view of the Investigator.

- Anaphylaxis, anaphylactoid, or other severe or life-threatening hypersensitivity reactions, based on the Investigator judgement.
- Use of a nonpermitted medicine, as defined in [Section 5.9.2](#). This should first be confirmed with the CRO Medical Monitor before discontinuation of the study drug.
- Noncompliance, judged as significant by the Investigator or Sponsor including noncompliance to the required study considerations, as defined in [Section 5.8](#).
- Surgery considered by the Investigator or Sponsor to be major (see [Section 4.2](#)).

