8.5.1 Delayed-Start Efficacy Analysis

The delayed-start analysis (Liu-Seifert et al., 2015; Wang et al., 2019) will be performed to evaluate potential disease modifying characteristics of the treatment. Week 24 and Week 48 data will be compared between Group 1 and Group 4. Group 1 (optimal dose treatment) is the early start group and Group 4 (placebo to optimal dose treatment) is the late start group. The analyses will include the following three comparisons:

- At Week 24, the change from baseline of an efficacy variable for Group 1 that achieves statistical significance compared with Group 4
- At Week 48, the change from baseline of an efficacy variable for Group 1 that achieves statistical significance compared with Group 4
- For the change from Week 24 to Week 48 of an efficacy variable, Group 1 is not inferior to Group 4

For continuous efficacy variables such as 6MWD, ANCOVA will be used with baseline 6MWD and randomization stratification factors as covariates. Normality will be examined using the Shapiro-Wilk test. If a normal distribution is rejected, a non-parametric Wilcoxon rank sum test stratified by stratification factors will be used. A multiple imputation method will be used to handle the missing data.

If Week 24 or Week 48 has missing data and subjects are still alive, a standard multiple imputation (MI) will be implemented using a regression model accounting for baseline 6MWD, randomization stratification factors, and if necessary, additional covariates such as demographic variables. For missing 6MWD data due to death, a random sample from the worst 10% change among all subjects will be used.

NT-proBNP is also a continuous variable; therefore, the delayed-start analysis will be performed similar to 6MWD.

The WHO function class improvement is a binary variable; therefore, the delayed-start analysis will be performed by Cochran-Mantel-Haenszel (CMH) test with randomization stratification factors as strata.

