8.5.2 Longer Term Analysis for the First Tier of Efficacy Endpoints

1) Overall survival throughout the parent trial and LTE study duration

Kaplan-Meier survival analysis will be performed. The probability of survival will be evaluated at one, three, and five (if there is sufficient follow-up time) years after initial study participation in the parent trial through the completion of the LTE trial.

A Cox regression analysis will be performed with baseline REVEAL Lite 2.0 category score and IPAH/HPAH or Non-IPAH/HPAH category. The hazard ratio and its 95% CI for the pairwise LTE treatment groups will be reported for Group 1 versus Group 4, Group 3, and Group 2 respectively.

2) Change from LTE baseline to post-LTE baseline in continuous effectiveness endpoints

The continuous endpoints measured at multiple timepoints include:

- Change from baseline in NT-proBNP
- Change from baseline in 6MWD
- Change from baseline in REVEAL Lite 2.0 Score
- Change from baseline in QoL emPHasis-10 Questionnaire score
- Change from baseline in Borg dyspnea index

The following analysis described for change from baseline in NT-proBNP will be used for the analysis of the continuous endpoints enumerated above.

The pairwise mean difference in change from LTE baseline among LTE treatment groups will be estimated using a mixed model for repeated measures (MMRM) model where the response is change from LTE baseline in an NT-proBNP at each post-baseline visit for each subject.

The explanatory variables will include:

- Fixed effect factors
 - Visit
 - LTE treatment groups
 - LTE treatment groups by visit interaction
 - IPAH/HPAH or Non-IPAH/HPAH category
- Fixed effect covariates
 - Continuous pre-LTE baseline value
 - Continuous parent trial baseline REVEAL 2.0 score
- Subjects as random effects

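### The delayed-start imputation model names neither treatment group nor the Week 24 value, so it shrinks the Week 48 Group 1 vs Group 4 difference by about the missing fraction

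*Combined protocol and SAP*

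**What the plan says.** Section 8.5.1 sets three comparisons of Group 1 with Group 4: superiority in change from baseline at Week 24, superiority at Week 48, and a third, "For the change from Week 24 to Week 48 of an efficacy variable, Group 1 is not inferior to Group 4". No non-inferiority margin is given. For walk distance, "ANCOVA will be used with baseline 6MWD and randomization stratification factors as covariates".

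For missing values in living subjects, "a standard multiple imputation (MI) will be implemented using a regression model accounting for baseline 6MWD, randomization stratification factors, and if necessary, additional covariates"; demographics are the example given. Values missing because of death follow a separate rule, a random draw from the worst tenth of changes. NT-proBNP is to be analysed in a similar way. Neither 8.5.1 nor any other section says that imputation is done by group or uses the Week 24 value. By contrast, the repeated-measures model in 8.5.2 lists treatment group, visit and "LTE treatment groups by visit interaction".

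Three other sections bear on which values will be missing:

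- Section 4.1 admits "Subjects who have successfully completed the placebo-controlled 24-week study AV-101-002 without a treatment-limiting toxicity resulting in discontinuation of study drug".
- Section 6 makes the parent study's Week 24 visit the LTE baseline visit.
- Section 6.8.1 gives subjects who stop drug two options: "discontinue from the study and agree to telephone contacts per the visit schedule", or leave and refuse further contact.

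**The concern.** An imputation model should contain every variable in the analysis model, above all the contrast being estimated. If group is absent, a Group 1 subject and a Group 4 subject with the same baseline and stratum receive Week 48 values from the same distribution. The imputed part of the data then shows no treatment difference, whatever the observed part shows. Leaving out the Week 24 value also discards the best predictor of Week 48, and one that would carry much of the group effect indirectly.

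The Week 24 comparison is little affected, because LTE entrants have completed the parent study and its Week 24 visit. The other two comparisons are both pushed against Group 1 when the true effect is positive. A benefit that lasts could be read as catch-up by Group 4, which is the distinction a delayed-start analysis exists to draw.

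**Working it through.** **Inputs.** The documents give the imputation predictors, the ANCOVA, the rule for deaths and the two-sided 0.05 level (section 8.5). They give no Group 1 or Group 4 size, SD, effect or missing rate for this analysis, so there is no planned figure to reproduce and every numerical input below is an assumption. Baseline is taken as the parent-study baseline, because section 8.4 exempts the delayed-start analysis from its general baseline rule.

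**Algebra.** Let D be the true Week 48 difference, m1 and m4 the fractions missing while alive in Groups 1 and 4 (completely at random), and w Group 1's share of observed subjects. Measured from the Group 4 mean, imputed values in both groups average wD. Then

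- Group 1 mean = (1 − m1)D + m1·wD
- Group 4 mean = m4·wD
- Estimated difference = D[1 − m1(1 − w) − m4·w]

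With m1 = m4 = m this is D(1 − m). With complete Week 24 data, the Week 24-to-48 difference is biased by −mD. With m1 = 30%, m4 = 10% and equal group sizes, w = 0.7/1.6 = 0.4375 and the factor is 1 − 0.3 × 0.5625 − 0.1 × 0.4375 = 0.788.

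**Simulation, main scenario.** Assumed: 100 per group, SD of change 60 m, Week 24/48 correlation 0.7, true difference 25 m at both visits, missing completely at random. There were 600 trials per scenario, with 20 proper imputations, Rubin's rules, and ANCOVA on baseline and one stratification factor.

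| Missing | 25(1 − m) | Week 48 difference as written | −25m | Week 24-to-48 as written (true 0) | Power as written | Power with group and Week 24 |
|---|---|---|---|---|---|---|
| 5% | 23.75 m | 23.9 m | −1.25 m | −1.1 m | 80% | 84% |
| 10% | 22.5 m | 22.4 m | −2.5 m | −2.6 m | 71% | 78% |
| 20% | 20.0 m | 19.8 m | −5.0 m | −5.1 m | 58% | 76% |
| 30% | 17.5 m | 17.0 m | −7.5 m | −7.8 m | 38% | 72% |

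With both variables added, the Week 48 difference is 24.5 to 25.3 m and the Week 24-to-48 difference is within 0.4 m of 0. At 20% missing, the standard error as written averages 9.5 m against an actual SD of the estimate of 7.8 m, so power is lost through the standard error as well as the shrinkage.

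Week 48 power at 5/10/20/30% missing for other group sizes:

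- 50 per group: 46/42/24/16% as written, 51/51/46/43% with both added.
- 150 per group: 94/90/79/62% as written, 96/94/92/91% with both added.

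With a true effect of 15 m, 20% missing and the model as written, the two differences are 11.7 m and −2.9 m (formula: 12.0 and −3.0).

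**Which omission matters.** Further runs (SD 75 m, D = 30 m, correlation 0.7, 100 per group, 500 trials, 10 imputations) give the ratio of estimated to true Week 48 difference, with Monte Carlo error about 0.016:

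| Missing | 1 − m | As written | Week 24 only | Group only | Both |
|---|---|---|---|---|---|
| 10% | 0.90 | 0.91 | 0.98 | 1.01 | 1.01 |
| 20% | 0.80 | 0.79 | 0.93 | 0.98 | 0.99 |
| 30% | 0.70 | 0.70 | 0.92 | 1.01 | 1.02 |
| 40% | 0.60 | 0.61 | 0.90 | 1.02 | 1.02 |

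Unequal missingness (30%/10% and 10%/30%) gives 0.80 and 0.79 as written, against the formula's 0.788. If subjects with poorer Week 24 values are more often missing (23% missing overall), the ratio is 0.73 as written, 0.95 with either variable alone and 1.01 with both.

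**Direction of error.** In the first set of assumptions, with a true Week 48 difference of 0, Week 48 rejection at 5/20/30% missing is 4/1/0% as written and 5/5/4% with both added. The planned method does not create false superiority here.

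**Subjects off drug.** If 20% are missing and Group 1 has no advantage among them, the true overall difference is 0.8 × 25 = 20 m. The model as written gives 20.3 m and the fuller model 25.5 m.

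**The case against.** The strongest reply is that silence on treatment group is a drafting habit here. The ANCOVA covariate list in 8.5.1 and the Cox model for survival in 8.5.2 also omit group, although both exist to compare groups. Section 8 calls itself an overview and leaves detail to a separate SAP, and the imputation list is open-ended. On this reading the plan is unspecified on group and does not exclude it. That is fair as far as group goes, and a later SAP could add both variables. But it does not supply the Week 24 value. The clause that could admit either variable is discretionary, with demographics as its only example.

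Other points stand in part:

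- If either variable alone were added, most of the shrinkage would go.
- The relevant fraction is narrower than total dropout. Deaths have their own rule, and the full analysis set needs a post-entry effectiveness measure, which drops the earliest losses. On the other hand, subjects with only an early LTE measure stay in and need imputing, and a calendar end date (31 December 2025, or the sponsor's decision) may stop late entrants before Week 48.
- In the off-drug scenario the model as written is close to the truth and the fuller model overstates benefit by more than a quarter (25.5 against 20 m). That agreement comes from an undeclared assumption that missing subjects have no group difference. It should be stated and tested openly.
- The error is conservative, and the analysis looks for potential disease modification in a study whose objective is long-term safety. This limits the severity.

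**Conclusion.** The concern holds. Followed as written, 8.5.1 biases two of its three delayed-start comparisons. The Week 48 difference shrinks by about the fraction missing while alive, and the Week 24-to-48 difference shifts by about that fraction of the true Week 48 difference. The proportional result is exact only for equal, completely random missingness. It becomes a weighted average when the fractions differ, and it can be somewhat worse when missingness depends on Week 24. The metres and power figures rest on assumed inputs. The problem is small at 5% missing and material from about 10 to 20% upward. The bias is toward no difference, so it costs power and weakens a true finding without producing a false one. The effect on the non-inferiority conclusion cannot be judged without a margin. This should be fixed before the analysis is run; it does not threaten the study's safety objective.

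**What to change.** State in 8.5.1 and the SAP that missing values in living subjects are imputed by sequential regression within treatment group, or with group in the model. The predictors should be baseline, the stratification factors and all observed values of the endpoint: Week 24, and the LTE Week 4 and Week 12 measurements that Table 1 already schedules for both walk distance and NT-proBNP. Keep the existing rule for deaths.

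This model assumes missing at random. Because subjects who stop drug leave the study with at most telephone contact, add a missing-not-at-random sensitivity analysis, for example delta-adjusted or reference-based.

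The cost is two sentences in 8.5.1 and the SAP and one extra sensitivity analysis. No new data are needed.

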8.4 Baseline and Demographics and Subject Study Disposition

With exception of the delayed-start analysis, for both the efficacy and safety analyses, baseline will be defined as the time prior to starting active treatment with AV-101 in either the LTE or the parent study. For Groups 1 and 2, since the subjects start receiving active treatment in the parent study, the baseline will be the values prior to first dose during the parent trial. For Groups 3 and 4, the subjects receive placebo in the parent trial and then receive active treatment in the LTE study, thus, the baseline will be the values prior to the first dose in LTE study.

Demographics and baseline data, medical and surgical history will be summarized using the screened analysis set. These demographics and baseline data will be presented by the LTE treatment groups as described in [Section 8.1](#).

Demographic and baseline data will be summarized using summary statistics of mean, standard deviation, median, lower quartile, upper quartile, min and max for continuous variables and number and percentage of subjects in each category.

Subject treatment status and study participation status will be reported for the safety analysis set. Subjects who completed all LTE assessments and early treatment discontinuation and withdrawal from the study including reasons for treatment or study discontinuation will be reported by LTE treatment groups.

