Unstructured covariance will be specified. If the fitted model does not converge with unstructured covariance, a simpler covariance will be specified. LSMeans by trial treatment groups and difference in mean change from baseline in NT-proBNP at each visit will be reported. At each post-baseline visit (with focus on Weeks 24, 48 and 72 after LTE entry) the difference in mean change from baseline in NT-proBNP between treatment groups and its 95% CI for the treatment term will be reported. The mean difference in change from LTE baseline between subjects always on the optimal dose will be compared in the following order: 1) always on placebo (Group 4); 2) placebo followed by an active treatment dose (Group 3); 3) always on the non-optimal dose (Group 2). Average treatment effectiveness before and after optimal dose treatment during the LTE will also be presented.

Trends in change from baseline (CFB) will initially be assessed graphically. To obtain a measure of trends using MMRM, visits as continuous variables, and visit by LTE treatment groups interactions will be entered into the model. The coefficient for continuous visit associated for each of the LTE treatment groups indicates the linear trend in change from baseline over visit. A non-linear trend in CFB will be tested by entering visit as quadratic or cubic spline of visit in the model.

3) Maintenance or improvement in WHO Functional Class throughout the LTE

At each post-LTE baseline visit, a subject's status with respect to remaining in or decreasing from the same WHO FC will be recorded. At each post-baseline visit, the proportion of subjects who remain or improve on their baseline WHO FC will be reported by treatment groups. A logistic regression model will be fitted where the response at each visit is whether the subject remains in or improves in WHO FC. The explanatory variables consist of LTE treatment groups, visit, LTE treatment groups by visit, IPA/HPA or non-IPA/HPA category, and continuous LTE baseline REVEAL Lite 2.0 score.

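### Neither WHO Functional Class analysis lists baseline class as its own term; in the long-term logistic model the REVEAL Lite 2.0 score is only a partial, and for Groups 1-2 mistimed, substitute

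*Combined protocol and SAP*

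**What the plan says.** **Delayed-start analysis (Section 8.5.1).** The endpoint is improvement: "The WHO function class improvement is a binary variable". For the comparison of Groups 1 and 4 on this endpoint, "the delayed-start analysis will be performed by Cochran-Mantel-Haenszel (CMH) test with randomization stratification factors as strata". The documents do not name those factors. For 6MWD in the same section, "ANCOVA will be used with baseline 6MWD and randomization stratification factors as covariates", and NT-proBNP is to be handled in a similar way.

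**Long-term analysis (Section 8.5.2, item 3).** In the logistic model, "the response at each visit is whether the subject remains in or improves in WHO FC". Its terms are then set out: "The explanatory variables consist of LTE treatment groups, visit, LTE treatment groups by visit, IPA/HPA or non-IPA/HPA category". The list ends with the REVEAL Lite 2.0 score at LTE baseline, as a continuous term. Odds ratios with 95% confidence intervals are reported for Group 1 against Groups 4, 3 and 2. By contrast, the repeated-measures model in item 2 lists "Continuous pre-LTE baseline value" as a covariate beside a REVEAL score.

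**Baseline visit (Section 8.4).** Except in the delayed-start analysis, Groups 1 and 2 take their baseline before the first parent-trial dose. Groups 3 and 4 received placebo in the parent trial; "thus, the baseline will be the values prior to the first dose in LTE study".

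**Availability.** Section 6.6.4 has FC assessed at all study visits, and Table 1 includes it at Screening/Baseline. Table 3 scores FC within REVEAL Lite 2: class I -1, class III +1, class IV +2.

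**The concern.** Starting class limits both FC responses. A class I subject cannot improve, and an observed class IV subject cannot worsen. Baseline class is therefore likely to be strongly prognostic, and the plan adjusts its continuous endpoints for just this kind of variable.

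The consequences differ between the two analyses. In the long-term model the reference class is taken at different times in different groups, so randomization does not guarantee the same class mix. A difference in mix can move the Group 1 versus Group 4 odds ratio away from 1 with no drug effect. In the delayed-start test, as far as Groups 1 and 4 keep the parent randomization, what is at stake is precision.

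**Working it through.** The plan gives no power, effect size, FC response rate, class mix or group size for either FC analysis, so there is no stated figure to reproduce. Everything below is illustrative.

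**1. What REVEAL carries, and when.** FC contributes between -1 and +2 points to a sum that also contains renal function, systolic pressure, heart rate, 6MWD and NT-proBNP. The sum enters as one linear term. For Groups 3-4 the LTE-baseline score is measured at the visit that sets their reference class. For Groups 1-2, under Section 8.4, the reference class is at parent entry while the score is taken 24 weeks later, on active drug. In those groups it does not contain the class from which change is counted, and it is a post-treatment variable.

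**2. Size of the bias in the long-term model.** Assume no treatment effect given class. With mix w and probability p of maintaining or improving in each class I to IV:

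P(group) = Σ w × p; crude OR = [P1/(1 − P1)] ÷ [P4/(1 − P4)].

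Example, with p = 0.75/0.85/0.92/0.99, Group 1 mix 0/40/57/3% and Group 4 mix 5/55/38/2%:

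- P1 = 0.3400 + 0.5244 + 0.0297 = 0.8941, odds 8.443
- P4 = 0.0375 + 0.4675 + 0.3496 + 0.0198 = 0.8744, odds 6.962
- crude OR = 8.443/6.962 = 1.21 (simulated 1.218)

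The simulation (400,000 per group) then adjusted either for a REVEAL-type score that includes the FC points or for FC categories. The stronger dependence uses p = 0.60/0.75/0.92/0.995.

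| Group 1 mix; Group 4 mix (I/II/III/IV, %) | Dependence on class | Crude OR | REVEAL-adjusted | FC-adjusted |
|---|---|---|---|---|
| 0/45/52/3; same | moderate | 1.003 | 1.004 | 1.004 |
| 0/45/52/3; same | strong | 1.001 | 1.002 | 1.004 |
| 0/45/52/3; 3/50/44/3 | moderate | 1.091 | 1.064 | 1.004 |
| 0/45/52/3; 3/50/44/3 | strong | 1.129 | 1.083 | 0.989 |
| 0/40/57/3; 5/55/38/2 | moderate | 1.218 | 1.146 | 1.003 |
| 0/40/57/3; 5/55/38/2 | strong | 1.352 | 1.230 | 0.998 |
| 0/35/62/3; 8/57/33/2 | moderate | 1.345 | 1.224 | 1.012 |
| 0/35/62/3; 8/57/33/2 | strong | 1.580 | 1.369 | 0.996 |

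The share of log-OR bias removed by REVEAL is 1 − ln(adjusted)/ln(crude). It runs from 1 − ln 1.064/ln 1.091 = 29% to 1 − ln 1.083/ln 1.129 = 34%. The simulated score is measured at the same visit as the reference class, so the mistiming in step 1 is not represented.

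**3. Direction.** The table assumes that Group 4 starts in better classes. Now suppose that Group 1 does, at 10/55/33/2% against 5/50/42/3%, with p = 0.70/0.85/0.94/1. Then P1 = 0.8677 and P4 = 0.8848, and the crude OR is 6.559/7.681 = 0.85, against the drug.

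**4. Power of the delayed-start CMH test.** Two-sided 0.05, conditional OR 2.2, 2,000 runs per scenario. Strata are aetiology by a binary risk category correlated with FC, first without and then with the four FC classes added. Control improvement rates for classes II/III/IV are 15/25/30% (weak), 8/30/45% (moderate) and 4/40/60% (strong).

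| Dependence on class | 60 per group | 100 per group | 150 per group |
|---|---|---|---|
| weak | 46.8 → 45.8% | 67.3 → 66.7% | 84.8 → 84.6% |
| moderate | 38.0 → 40.3% | 59.2 → 61.6% | 77.2 → 78.8% |
| strong | 25.5 → 32.4% | 43.8 → 52.4% | 59.7 → 70.4% |

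The gain is nil under weak dependence, about 2 points under moderate and 7 to 11 under strong. With a true OR of 1, rejection rates were 4.1% to 5.6% across tests with and without FC.

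**The case against.** A reader might infer that the plan ignores baseline FC altogether. The documents do not support that. The long-term model includes REVEAL Lite 2.0, which scores FC, so adjustment there is partial rather than absent. The CMH strata come from parent randomization factors that are not named here, and FC or a risk category containing it may already be one of them.

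A reader might also take crude odds ratios such as 1.21 or 1.35 as what the planned model would report. They are not: the planned model includes REVEAL, which shrinks them. Nor is the CMH test invalid or shown to be short of power. It is a valid test, no power is claimed for it, and the study's main objective is long-term safety. An added stratum improves efficiency and may create sparse tables.

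The reference visit for item 3 is also open to question. Section 8.4 points to parent entry for Groups 1-2, but item 3 speaks of the LTE period and uses an LTE-baseline score, and item 2 counts change from LTE baseline. If LTE baseline applied to every group, the timing mismatch would disappear. The mix could still differ, because Group 1 would have had 24 weeks of active drug and Group 4 placebo.

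Finally, FC is not singled out. The Wilcoxon fallback for 6MWD names no baseline covariate, and the multicomponent model relies on REVEAL rather than component baselines. The statement that class IV cannot fail applies only to observed subjects, since the scoring of death is not given.

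These points limit the claim. They do not supply the missing term in item 3, whose covariates are listed.

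**Conclusion.** The point stands, mainly for Section 8.5.2(3). Adjustment for starting class is indirect, and under the baseline rule of Section 8.4 the score is taken at the wrong visit for Groups 1-2. If class mix differs between groups, the Group 1 versus Group 4 odds ratio is biased. In the scenarios with unequal mix and a true odds ratio of 1, about 1.06 to 1.37 remained after REVEAL adjustment, against about 1.00 with categorical FC. With equal mix there is no bias. The documents give no FC distribution, so neither size nor direction can be predicted.

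For Section 8.5.1 the point is secondary and conditional on FC not already being a stratum. It concerns efficiency, about 0 to 11 power points depending on how strongly improvement depends on class. The test as planned has no type I error problem, as far as Groups 1 and 4 keep the parent randomization. All class rates, mixes, effect sizes and group sizes used here are assumptions.

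**What to change.** 1. **Section 8.5.2(3).** State which visit defines the reference class in each group. Add WHO FC at that visit as a categorical factor in the logistic model, pooling sparse classes.
2. **Section 8.5.1.** Name the parent randomization stratification factors. If they do not include FC, add parent-baseline FC (I-II versus III-IV) as a CMH stratum.

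The cost is SAP wording. Section 8 already leaves analysis detail to the SAP, FC is already collected, and trial conduct does not change. The drawback is some sparse strata once FC is crossed with the other factors, which is why the two-level grouping is suggested.
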